7.1 Ethical Considerations: Informed Consent/Accent and HIPAA Authorization

A compound consent form will be used (see attached).

7.2 Institutional Review Board (IRB) Review

IRB approval will be required prior to study enrollment.

7.3 Subject Confidentiality

Protecting Confidentiality: To ensure confidentiality, all participant research records will be kept in locked files in the Department of Psychiatry at the Yale University School of Medicine or on secure server at Yale. All research forms, interviews, measures, audiotapes, and computer data will be coded to ensure anonymity and will be kept in separate locked files. Data analysis and reporting will not allow for identification of any individual participants. All research personnel will be trained and supervised around confidentiality issues. The training will include formal Yale IRB modules with testing certification as well as HIPAA guidelines to follow around confidentiality. All information collected will remain confidential except when we are legally required to disclose such information by law. These circumstances include knowledge of abuse of a child or elderly person, threats of harm to self or others, and plans to harm to property. Research records may be the subject of an audit by a regulatory agency. Organizations which have a responsibility for protecting human subjects, including the Yale Human Investigation Committee (HIC), may have access to the research records. Additionally, the funding agency (APF) may have access to the research records. The

subject's identity will remain protected except as required for legal or regulatory inquiries. Individually identifiable health information will be protected in accordance with the Health Insurance Portability and Accountability Act of 1996. All research personnel will be trained on HIC and HIPAA procedures.

7.4 Deviations/Unanticipated Problems

Deviations/unanticipated problems will be reported to the IRB.

7.5 Data Collection

Data collection is done by study staff who received and completed Yale trainings in human subjects, HIPAA, and good clinical practice and are approved by the HIC.

7.6 Data Quality Assurance

Data is cleaned and monitored by the study team.

7.7 Study Records

All participants will be assigned a study ID. Subsequently, participants will be identified only by that ID. A list of numbers and the corresponding names will be maintained by investigators on a protected research server. Any identifying information that is collected on paper will be kept in locked research cabinets within a locked suite. Interviews will be recorded using a digital recorder and recordings will be securely and separately stored and be identified only by a study ID and date. Data will be saved on a secure server. Any information published as a result of the study will be such that it will not permit identification of any participant. All information collected will remain confidential except when we are legally required to disclose such information by law. These circumstances include knowledge of abuse of a child or elderly person, threats of harm to self or others, and plans to harm to property.

7.8 Access to Source

7.9 Data or Specimen Storage/Security

Data are stored on a secure server and in locked file cabinets on a secure floor and building.

7.10 Retention of Records

Data will continue to be stored in locked cabinets in limited access areas until the legal requirement for storage has been met. Electronic data files will be password protected. Electronic data files will include code numbers only — i.e., will not contain patient identifying information.

7.11 Study Monitoring

Monitoring for data integrity and safety will be the responsibility of the investigators and the Yale IRB (Human Investigation Committee). The data safety monitoring plan (DSMP) for this clinical trial focuses on close monitoring by the principal investigator and co-investigators.

7.12 Data Safety Monitoring Plan

The investigators will perform study oversight and monitoring including data quality, storage, confidentiality, and issues covered in good clinical practice. In addition, the principal investigator will promptly report excessive adverse events and any serious adverse events to the APF and to the IRB at the Yale University School of Medicine. Other (less serious) adverse events will be reported to the IRB periodically during regular reporting periods.

The principal investigator is responsible for monitoring the data, assuring protocol compliance, and conducting the safety reviews quarterly. During the review process the principal investigator will evaluate whether the study should continue unchanged, require modification/amendment, or close to enrollment.

The principal investigator and co-investigators will review the following:

1. Recruitment and retention for the study and compare them to target rates.
2. Rates of data completeness and availability of primary outcome data
3. Occurrence of AEs and SAEs
4. Report of study progress since the last report.
5. Rates of recruitment of women and minorities with respect to targets.

These reports are generated by the study coordinator each quarter (reviewed by PI and co-investigators). If adverse events occur in greater magnitude or frequency than expected these will be reported to the APF and HIC prior to scheduled reports. The Principal Investigator will assume full responsibility for reporting serious and non-serious and unanticipated adverse events.

Because the projected effect sizes may not be large enough for detection during interim analyses, we are not proposing a preliminary analysis of accumulating efficacy and safety data by treatment assignment. Instead, we will review twice-yearly aggregate data that contains screening data, baseline demographics, retention data, serious adverse events data, as well as accrual status, and any other data that will help in the assessment of the clinical trial.

Risk Assessment:

The risks associated with the current study are deemed greater than minimal. Although we do not view the risks associated with the study medication as minimal risk, the established safety and validity of the Naltrexone/Bupropion (FDA-approval of Contrave for obesity) RCTs suggest that the study procedures and medications are not high risk.

Although we have assessed the proposed study as one of greater than minimal risk, the potential exists for anticipated and/or unanticipated adverse events, serious or otherwise, to occur since it is not possible to predict with certainty the absolute risk in any given individual. Therefore, we provide a plan for monitoring the data and safety of the proposed study as follows:

Measurement and reporting of adverse events.

Adverse event data will be collected on an on-going basis. Adverse events data will be reviewed by the PI and co-investigators throughout this trial (see Table below). A summary of adverse events will be provided to the Yale IRB yearly during the annual renewal review process. Any serious or unanticipated adverse events will be reported to the NIH and to the Yale IRB within 48 hours.

The frequency of data review is summarized in the following table:

Table	Data type	Frequency of Review by PIs and Research Team
Table 1	Subject accrual	Monthly
Table 2	Treatment completion rates (retention/attrition)	Quarterly
Table 3	Adverse and serious adverse event rates	Quarterly
Table 4	Checklist for DSMB	NA

Attribution of Adverse Events:

Adverse events will be monitored for each subject participating in the study and attributed to the study procedures by the investigators according to the following categories:

1. Definite: Adverse event is clearly related to the investigational procedure/agent.
2. Probable: Adverse event is likely related to the investigational procedure/agent.
3. Possible: Adverse event may be related to the investigational procedure/agent.
4. Unlikely: Adverse event is likely not to be related to the investigational procedure/agent.
5. Unrelated: Adverse event is clearly not related to the procedure/investigational agent.

Plan for Grading Adverse Events:

The following scale will be used in grading the severity of adverse events noted during the study:

1. Mild adverse event
2. Moderate adverse event
3. Severe adverse event resulting in inpatient hospitalization or prolongation of existing hospitalization, a persistent or significant disability/incapacity, or a congenital anomaly/birth defect.
4. Severe adverse event that may jeopardize the participant's health and requires medical or surgical intervention to prevent death, disability/incapacity, or congenital anomaly.
5. Fatal adverse event

Plan for events to the Yale IRB that are unexpected AND related AND involve risk of harm to subjects or others:

The PI will report any incident, experience, or outcome that meets all three of these conditions to the IRB immediately: a) unexpected (in nature, specificity, severity, or frequency); b) related (probably or definitely); and c) places participants or others at greater risk of harm (physical, psychological, economic, legal, or social) than previously known or recognized. Following immediate reporting, an event will be reported using Form 710 FR 4 (Unanticipated Problem Involving Risks to Subjects or Others Reporting Form) to the IRB within 5 calendar days of it becoming known to the PI.

Plan for reporting adverse events to co-investigators on the study, as appropriate the protocol's research monitors, e.g., study sponsors, funding and regulatory agencies, and regulatory and decision-making bodies:

For the current study, the following individuals, funding, and/or regulatory agencies will be notified:

1. All Co-Investigators listed on the protocol
2. American Psychological Foundation

The investigators will conduct a review of all adverse events upon completion of every study subject. The investigators will evaluate the frequency and severity of the adverse events and determine if modifications to the protocol or consent form are required.

Procedures for providing follow up care:

Medical monitoring will occur at all clinic and follow up visits and medical care will be provided if warranted. If a study participant experiences any psychiatric symptoms or distress (e.g., depressive symptoms or suicidality) at any stage of study participation he/she will receive short-term treatment and support from the study treatment team (including

psychologists) and will be connected to a local emergency department (e.g., the Crisis Intervention Unit at Yale-New Haven Hospital) and his/her physician or therapist for ongoing care.

Measurement and reporting of subject accrual, adherence to inclusion/exclusion criteria.

Review of the rate of subject accrual and adherence to inclusion/exclusion criteria will occur regularly by the PI and co-Investigators. These reviews will help to assure that participants meet eligibility criteria and ethnic diversity goals.

Measurement and reporting of participant treatment completion rates.

Participation rates (retention and attrition) will be reviewed on an ongoing basis by the PIs and co-investigators to identify any potential problems, and formally twice-yearly. Any differential dropout and/or higher than expected dropout will be reviewed by the investigators to determine whether any problems are present and what, if any, corrective action needs to be taken.

During the reviews, if the investigators have concerns about whether attrition has reached a level that might inhibit the ability of the study to address its primary aims, they will suggest a meeting to discuss methods for improving subject retention. Previous pharmacotherapy studies for binge-eating disorder and obesity (with comparable time frames for pharmacotherapy) have reported attrition rates between 20% and 38%. Studies of NB for obesity treatment reported attrition of 30% to 45%. Thus, "trigger points" for review and discussion by principal investigator and research staff will be: 35% ("low alert"), 40% ("mid alert"), 45% ("high alert"), 50% ("extreme alert"). With early alerts to problems, action would be taken to avoid higher level alerts; if a higher level alert should arise, more drastic actions would be taken.

Trial Stopping Rules

Given that this study is deemed greater than minimal risk to human subjects, it is more likely that attrition or difficulty in recruiting adequate numbers of participants will require stopping the trial than would excess adverse events. However, as outlined, adverse events will be monitored in all participants, and the PI will alert the Yale IRB and the APF if a larger (or more serious) than reasonably expected adverse event rate should occur. Other potential issues relating to stopping rules for this trial include:

1. New Information

It is unlikely that any new information will become available during this trial that would necessitate stopping the trial. If new safety data (i.e., pertaining to short-term use of the study medication) become available, this will be evaluated.

1. Limits of Assumptions

It is possible that excessive attrition and/or missing data could limit the value of data analysis. This will be evaluated yearly and if present, considered in relation to potential effects on the power to detect differences in the primary outcomes.

The following actions would be taken at each level of alert:

- (1) Low-level alert = Review of potential problems by PI.
- (2) Mid-level alert = Meeting with co-investigators to discuss approaches to minimize further losses to follow-up/dropouts.
- (3) High-level alert = Meeting with co-investigators to determine further alterations of study protocol to complete the study with no further losses.
- (4) Extreme-level alert = In the unlikely event of a 50% dropout rate prior to the mid-study time point, discontinuing the trial would be considered.

1. Limits of Rules

There are other situations that could occur that might warrant stopping the trial and/or including a section on the safety report entitled "Other situations that have occurred since the last safety report that warrant discussion" to allow for communication of concerns.

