Risks. Several large-scale studies have found that this medication is safe and effective for the treatment of obesity [Rusch & Andris, 2007; Elder et al., 2008; Mond et al., 2010; Citrome, 2015]. The NB combination approved by the FDA (Contrave) is reported to have the following common adverse reactions: nausea (32.5%), constipation (19.2%), headache (17.6%), vomiting (10.7%), dizziness (9.9%), insomnia (9.2%), dry mouth (8.1%), and diarrhea (7.1%). In addition, Contrave will have the FDA warnings and precautions: Suicidal Behavior and Ideation: Monitor for depression or suicidal thoughts. Discontinue medication if symptoms develop. Risk of seizure may be minimized by adhering to the recommended dosing schedule and avoiding co-administration with high-fat meal. Increase in Blood Pressure and Heart Rate: Monitor blood pressure and heart rate in all patients, especially those with cardiac or cerebrovascular disease. Hepatotoxicity: Cases of hepatitis and clinically significant liver dysfunction observed with naltrexone exposure. Angle-closure glaucoma: Angle-closure glaucoma has occurred in patients with untreated anatomically narrow angles treated with antidepressants. Use of Antidiabetic Medications: Weight loss may cause hypoglycemia. Monitor blood glucose. Warning about Opioid Withdrawal: We will include this advisory pertaining to opioid use and examples of opioid-based medications and drugs in the written consent form as well as the verbal consent process: *Naltrexone can cause withdrawal symptoms in individuals who are taking opioid pain medications or drugs. You should not participate if you are taking opioid medications of any kind and we will not include you in the study if we know or suspect you are using opiate-containing drugs.* In addition to structured clinical diagnostic interviews with our clinical-research staff and medical record reviews, we will perform lab urine test at Quest with potential subjects suspected of opiate usage.

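### The adverse-event severity scale in Section 7.12 ties its severe grades to seriousness outcomes, so a side effect that is severe in intensity alone falls to moderate

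*Combined protocol and SAP*

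**What the plan says.** Section 7.12 (Plan for Grading Adverse Events) introduces the scale with the words "The following scale will be used in grading the severity of adverse events noted during the study". Its five levels are:

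- Grade 1: "Mild adverse event", with no criterion.
- Grade 2: "Moderate adverse event", with no criterion.
- Grade 3: "Severe adverse event resulting in inpatient hospitalization or prolongation of existing hospitalization, a persistent or significant disability/incapacity, or a congenital anomaly/birth defect".
- Grade 4: "Severe adverse event that may jeopardize the participant's health and requires medical or surgical intervention to prevent death, disability/incapacity, or congenital anomaly".
- Grade 5: a fatal event.

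Later in Section 7.12, after each participant completes, all adverse events are reviewed: "The investigators will evaluate the frequency and severity of the adverse events and determine if modifications to the protocol or consent form are required". The same section makes severity one of the respects in which an event can count as unexpected. Being unexpected is one of three joint conditions for immediate reporting to the IRB.

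Two other sections foresee side effects bad enough to change or end NB. Section 3.3.1 refers to side effects that are too severe, and Section 6.1.2 to side effects that cannot be tolerated. Neither mentions hospital admission or any other serious outcome.

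**The concern.** Severity is how intense an event is. Seriousness is what the event led to or threatened. The scale is named for the first, but from grade 3 upward it is defined partly by the second. An event that is severe in intensity, handled wholly as an outpatient and without a serious outcome then has nowhere to go but moderate. There it shares a grade with events that participants could live with.

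The severity judgement has a stated use, since it informs whether the protocol or consent form should change. The pilot is also meant to inform larger trials of NB after bariatric surgery. It uses immediate-release bupropion because surgery can alter drug absorption (Section 6.1.2), so how intense the side effects are in this population is worth recording accurately.

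**Working it through.** The plan states no figure on this point, so there is nothing to reproduce. The check is whether the five grades cover every kind of severe event.

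| Event, severe in intensity | Grade 3 condition met? | Grade 4 condition met? | Grade available |
|---|---|---|---|
| Leads to admission or a longer stay | Yes | Depends on the event | 3 (or 4) |
| Outpatient, with significant or lasting disability or incapacity | Yes | Depends on the event | 3 (or 4) |
| Outpatient, needs intervention to prevent death, disability or anomaly | Depends on the event | Yes | 4 (or 3) |
| Outpatient, none of the above (e.g. repeated vomiting or severe insomnia that ends NB) | No | No | 2 at most |

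The last row is the gap. Sections 3.3.1 and 6.1.2 show that the protocol expects side effects of this kind. An event can therefore be too severe for NB to continue under Section 3.3.1 and at most moderate under Section 7.12.

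The order of the upper grades points the same way. An event that causes persistent disability is grade 3, while one that needs intervention to prevent disability is grade 4. That is not a ranking by intensity.

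**Illustration of where events would fall.** The number who will start NB is not stated. I assume 5 to 20 of the 25 participants. The rates are the documents' own: nausea 32.5% and vomiting 10.7% (Section 6.1.1), and serious adverse events on NB 1.6% (Section 3.3.1). Expected count = n × p; chance of at least one = 1 − (1 − p)^n.

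- Nausea: 5 × 0.325 = 1.6 to 20 × 0.325 = 6.5 participants.
- Vomiting: 5 × 0.107 = 0.5 to 20 × 0.107 = 2.1 participants.
- Serious adverse event: 5 × 0.016 = 0.08 to 20 × 0.016 = 0.32 participants; chance of at least one 1 − 0.984^5 = 7.7% to 1 − 0.984^20 = 27.6%.

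If these rates carry over and grades 3 to 5 track seriousness, those grades will most likely be empty and nearly all NB side effects will sit in the two grades without descriptors. The nausea and vomiting rates cover events of any severity, so these counts do not measure how many would be misgraded. The documents give no rate of severe but non-serious events, and that number cannot be derived.

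**The case against.** The strongest case on the other side is that the gap is narrow and that little depends on the grade. Several stronger readings are tempting, and the documents do not support them.

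- *A reader might infer that such an event has no grade at all.* Grade 2 has no criterion and can take it. The event is down-graded, not left ungraded.
- *A reader might infer that every outpatient event is confined to grades 1 and 2.* Grade 4 does not require admission, and grade 3 can also be met through disability or incapacity. Incapacitating nausea in an outpatient could arguably be grade 3.
- *A reader might infer that a modest event with a precautionary admission becomes grade 3.* Grade 3 also requires the event to be severe, so on its words it does not.
- *A reader might infer that tolerability will be under-reported.* Adverse events are collected by checklist at clinic visits (Section 6.2) and continuously (Section 7.12), whatever their grade. The 48-hour report is triggered by an event being serious or unanticipated. Stopping NB for intolerance is a defined event (Section 6.1.2), and pill counts and completion rates are also followed. Treatment-ending side effects can thus be seen without the grade.
- *A reader might infer that the pilot will show few severe events because of the scale.* With a 1.6% serious-event rate and so few participants, grades tied to seriousness would be sparse anyway. How many intensity-severe events the scale would hide is unknown.

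It is also fair to say that Section 7.12 already reviews adverse and serious adverse event rates, that tolerability is not a listed outcome (Section 5.2.1), and that Section 6.4.1 plans no analysis by grade.

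All of this limits the consequence but does not remove the defect. The scale is the only severity instrument described. The review after each participant, and the severity part of the unexpectedness condition, both need a severity judgement. The documents do not say that the unexpectedness judgement is made by grade, but they offer no other measure.

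**Conclusion.** The grading rule is wrong as written, and the priority is minor. Applied exactly, it places an NB side effect that is severe in intensity, but free of the grade 3 and grade 4 conditions, in an undefined moderate category. The severity profile available to the investigators for decisions on the protocol and consent form may therefore be understated.

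The coverage gap follows from the wording alone and needs no numerical assumption. Its size cannot be given. The illustrative counts rest on an assumed 5 to 20 NB starters and on rates quoted from other NB populations. Event capture, the 48-hour serious-event report and the planned estimates of percent weight loss are unaffected.

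**What to change.** In Section 7.12:

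1. Grade severity as mild, moderate or severe, with a short descriptor for each based on intensity or effect on usual activity, regardless of outcome.
2. Record seriousness as a separate yes/no item, using the existing hospitalisation, disability, birth-defect, intervention and fatal text as its criteria.
3. For each event, record the action taken on NB (none, reduced, stopped). This documents what was done and changes no rule about when NB is reduced or stopped.
4. Base the review after each participant, and the final report, on both severity and seriousness.

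The cost is minor wording in Section 7.12 and on the adverse-event form. That form is not in the documents, so some of these items may already be on it. No extra visits or staff are needed. The one visible downside is that the reported count of severe events may rise slightly.
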